# Evaluation of low-cost techniques for detecting sickle cell disease and $\beta$ -thalassemia in Nepal

# 1.0 Background

## 1.1 Sickle cell disease

Sickle cell disease (SCD) is a collection of inherited blood disorders, and is a multisystem disorder affecting nearly every organ in the body [1]. The disease primarily causes erythrocytes or red blood cells (RBCs) to be distorted and rigid due to polymerization (e.g. during deoxygenation), often changing them to crescent or sickle shaped cells [2]. Other cascading effects include hemolytic anemia, blockage of microvasculature (capillaries and small blood vessels), episodes of acute illness (such as vaso-occlusive pain crisis or sickle cell crisis), and progressive organ damage [3], [4]. The chances of survival and quality of life drastically increase with early diagnosis, newborn screening, penicillin prophylaxis, pneumococcal immunization, blood transfusion, hydroxyurea treatment, hematopoietic stem-cell transplantation, and education about disease severity and complications [1], [4].

SCD is one of the most common monogenic diseases worldwide and results from mutations in the  $\beta$ -globin gene [1], [3]. The most common and severe form of SCD is sickle cell anemia (SCA), caused by the inheritance of  $\beta^S$  alleles or the variant HbS (hemoglobin S or sickle hemoglobin) genes from both parents – resulting in the homozygous form HbSS, instead of the normal homozygous form HbAA. Another form of SCA is HbS/ $\beta^0$  thalassemia, caused by the inheritance of a  $\beta^0$  thalassemia mutation from one parent and an HbS gene from another, resulting in no normal HbA and a majority of HbS. The heterozygous form HbAS, known as sickle cell trait (SCT), affects millions of people worldwide and is usually not associated with hematological abnormalities [2]. On the other hand, compound heterozygous conditions are associated with mild to severe clinical courses and are also categorized as SCD. Some compound heterozygous conditions include HbS with hemoglobin C or HbC (HbSC), HbS with  $\beta$ -thalassemia (HbS/ $\beta^0$ -thalassemia or HbS/ $\beta^+$ -thalassemia), and HbS with other  $\beta$  globin variants (e.g. HbSD and HbSOArab) [1], [3], [4].

An increasing global health problem, SCD is associated with an estimated 300,000 to 400,000 births every year [5]. The prevalence of the disease is high in sub-Saharan Africa, the Middle East, the Mediterranean basin and the Indian subcontinent, mainly due to the remarkable survival advantage of the sickle cell trait against severe malaria ("malaria hypothesis") [1]. It is estimated that people with SCT (heterozygous HbAS) are 90% less likely to experience severe malaria than individuals with normal hemoglobin [5] – making the malaria hypothesis a classic example of natural selection and balanced polymorphism [1]. The sickle hemoglobin allele (HbS) has spread beyond malaria-endemic regions due to population movements (including slave trading), especially to regions in North America and Western Europe [5]. Additionally, gene frequencies of  $\alpha$  and  $\beta$  thalassemia can be greater than 80% in malaria-endemic regions [2].

#### 1.2 Thalassemia and its interaction with sickle cell disease

Hemoglobin is the protein in red blood cells that transports oxygen (and carbon dioxide) between lungs and other tissues/cells in the body. The hemoglobin molecule is made up 4 polypeptide chains or subunits, such as alpha, beta, gamma or delta chains. The three most common types of hemoglobin are hemoglobin A (normal adult hemoglobin), hemoglobin F (fetal hemoglobin), and hemoglobin A2 (normally found in small quantities in adults). Hemoglobin A is

made up of 2 alpha chains and 2 beta chains ( $\alpha_2\beta_2$ ). Hemoglobin F is made up of 2 alpha chains and 2 gamma chains ( $\alpha_2\gamma_2$ ). Hemoglobin A2 is made up of 2 alpha chains and 2 delta chains ( $\alpha_2\delta_2$ ).

Thalassemia is an inherited condition which results in a deficiency or abnormality in the synthesis of one or more of these polypeptide/globin chains or subunits. Clinical symptoms include anemia resulting from inadequate hemoglobin synthesis, and ineffective production of red blood cells due to an unbalanced accumulation of one of the globin chains.  $\alpha$ -thalassemia is caused by mutations in the alpha globin genes. Since each chromosome normally has 2 alpha genes, there are four possible syndromes related to  $\alpha$ -thalassemia with increasing severity caused due to 1 to 4 genes being absent or failing to function: 1)  $\alpha^+$  thalassemia trait, 2)  $\alpha^0$  thalassemia trait, 3) hemoglobin H disease, and 4) hemoglobin Bart's hydrops fetalis.  $\beta$ -thalassemia is caused by mutations in the beta globin genes. Although there are more than 400 mutations identified, the majority of cases either result in a reduced ( $\beta^+$ ) or absent ( $\beta^0$ ) production of beta chains. Based on the clinical severity, thalassemia is also classified as thalassemia minor or trait (where individuals are silent carriers and asymptomatic), thalassemia intermedia (associated with mild anemia and is transfusion independent), and thalassemia major (associated with anemia and is transfusion dependent) [2].

The interaction and clinical severity of sickle cell with  $\beta$ -thalassemia depends on the type of  $\beta$ -thalassemia gene inherited. Coinheritance of HbS and  $\beta^+$ -thalassemia results in mild sickling disorder, while coinheritance of HbS and  $\beta^0$ -thalassemia results in severe sickle cell disease. The clinical symptoms and test results of HbS/ $\beta^0$ -thalassemia is similar to HbSS (homozygous SCD) because both cases predominantly have HbS and no HbA, which makes it difficult to distinguish the two cases. The clinical syndromes and levels of anemia related to HbSS and  $\alpha$ -thalassemia are generally less severe than those related to HbS/ $\beta^0$ -thalassemia. Generally, a distinction between HbSS with and without  $\alpha$ -thalassemia is clinically not required. The interaction of HbS with other hemoglobin variants such as HbDPunjab or HbOArab also results in severe sickle cell disease [2].

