## 6.3 Statistical Analysis Plan

Considering HPLC as the reference test, the sensitivity, specificity, positive predictive value (PPV) and negative predictive value (NPV) of the index tests or low-cost techniques (automated

sickling test, HbS solubility test, HemoTypeSC, Sickle SCAN, and Gazelle Hb variant test) will be evaluated.

For each case, the following definitions apply:

- True positive (TP): indicates a positive result for both the index test and the reference test
- True negative (TN): indicates a negative result for both the index test and the reference test
- False positive (FP): indicates a positive result for the index test, but a negative result for the reference test
- False negative (FN): indicates a negative result for the index test, but a positive result for the reference test

The following metrics will be calculated using the total number of TP, TN, FP, and FN:

Sensitivity = 
$$\frac{TP}{TP + FN} \times 100\%$$
  
Specificity =  $\frac{TN}{FP + TN} \times 100\%$   
 $PPV = \frac{TP}{TP + FP} \times 100\%$   
 $NPV = \frac{TN}{TN + FN} \times 100\%$ 

The metrics (sensitivity, specificity, PPV, and NPV) for the index tests will be calculated for the following two categories:

- 1. **Detection analysis by hemoglobin variant** (HbA, HbS, HbC, β-thalassemia): Heterozygous or homozygous forms containing a particular hemoglobin variant in both the index test and the reference test are true positive results for that variant. Test results lacking a particular hemoglobin variant in both index and reference tests, irrespective of other variants present, are true negative results for that variant. The following hemoglobin variants will be analyzed for the index tests.
  - HbS Solubility: HbA, HbS
  - Automated sickling: HbA, HbS
  - HemoTypeSC: HbA, HbS, HbC
  - Sickle SCAN: HbA. HbS. HbC
  - Gazelle Hb Variant: HbA, HbS, HbC, β-thalassemia
- 2. **Detection analysis by phenotype**: In this analysis, the metrics for homozygous and heterozygous states will be calculated differently. The following phenotypes will be analyzed for the index tests.
  - Automated sickling: HbAA, HbAS, HbSS, Overall
  - HemoTypeSC: HbAA, HbAS, HbSS, (HbAC, HbSC, HbCC), Overall
  - Sickle SCAN: HbAA, HbAS, HbSS, (HbAC, HbSC, HbCC), Overall
  - Gazelle Hb Variant: HbAA, HbAS, HbSS, HbS/β-thalassemia, HbA/β-thalassemia, Hbβ/β-thalassemia, (HbAC, HbSC, HbCC), Overall

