#### 7.5.5 HPLC

HPLC will be performed using the same technique used for routine tests for patients at the hospital/clinic. Each test uses approximately 5  $\mu$ L of whole blood.

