For this study, the machine learning algorithm will not be used to diagnose new patients, and the ground truth will be derived from results from the gold standard test (HPLC). The images of blood cells will be trained/tested using results from HPLC as the ground truth (e.g. diagnosis of sickle cell trait).

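### Where HbA is absent, Gazelle results for HbSS versus HbS/β-thalassemia show agreement with HPLC, not accuracy for the true phenotype

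*Combined protocol and SAP*

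**What the plan says.** Section 6.3 (Statistical Analysis Plan) defines every accuracy metric against a single method: "Considering HPLC as the reference test, the sensitivity, specificity, positive predictive value (PPV) and negative predictive value (NPV) of the index tests" are to be evaluated, with no second method for any phenotype. The phenotype analysis for Gazelle lists "Gazelle Hb Variant: HbAA, HbAS, HbSS, HbS/β-thalassemia, HbA/β-thalassemia, Hbβ/β-thalassemia, (HbAC, HbSC, HbCC), Overall", so HbSS and HbS/β-thalassemia are scored as separate categories. The variant-level analysis also scores Gazelle on β-thalassemia as such. Section 7.2.1 plans 20 participants in each of the two groups and does not divide HbS/β-thalassemia into β0 and β+.

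Section 1.2 says that HbS/β0-thalassemia resembles HbSS clinically and on testing, since both show mostly HbS and lack HbA, "which makes it difficult to distinguish the two cases".

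On how the reference call is made, section 7.5.5 says only that "HPLC will be performed using the same technique used for routine tests for patients at the hospital/clinic". Section 7.7 leaves interpretation to doctors at the site. Neither section gives a rule for assigning a sample with HbS and no HbA to one group or the other.

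**The concern.** The plan asks the reference method to make a distinction that its own background section calls difficult, for a reason that lies in the hemoglobin pattern itself. If HPLC puts an HbS/β0 sample under HbSS, an index test that reads it correctly is charged with an error. If Gazelle, an electrophoresis test that also works from separated hemoglobins (section 1.6), makes the same mistake, the shared error is counted as a success. The bias can go either way, and the planned data cannot show which.

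Accuracy is the primary endpoint (section 5.0), Gazelle is the only index test scored on HbS/β-thalassemia, and compound forms are part of the reason for the study (sections 1.4 and 1.8). A published sensitivity for HbS/β-thalassemia would be read as the chance of recognising that condition.

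**Working it through.** **Plan's own figure.** Section 6.3 gives about 120 participants: 6 groups × 20 = 120, which reproduces. The documents state no precision target and no HPLC error rate.

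**Inputs.** There are 20 participants per group (section 7.2.1), taken here as 20 per HPLC label. For β-thalassemia at variant level, reference positives are HbS/β, Hbβ/β and HbA/β (3 × 20 = 60), and reference negatives are HbSS, HbAS and HbAA (3 × 20 = 60).

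**Assumption.** Let x be the number of the 20 HPLC-labelled HbSS who are truly HbS/β0. No document supports a particular x, so 1 to 5 is shown. All other labels are taken as correct.

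**Case A: Gazelle makes no errors.**
- HbSS sensitivity = (20 − x)/20
- HbS/β-thalassemia specificity = (100 − x)/100
- Variant-level β-thalassemia specificity = (60 − x)/60
- Overall accuracy = (120 − x)/120

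**Case B: Gazelle repeats every HPLC error.** All apparent figures are 100%. True HbS/β-thalassemia sensitivity = 20/(20 + x).

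| x | A: HbSS sensitivity | A: HbS/β specificity | A: β-thalassemia specificity (variant) | A: overall | B: apparent | B: true HbS/β sensitivity |
|---|---|---|---|---|---|---|
| 1 | 19/20 = 95.0% | 99.0% | 59/60 = 98.3% | 119/120 = 99.2% | 100% | 20/21 = 95.2% |
| 2 | 18/20 = 90.0% | 98.0% | 58/60 = 96.7% | 118/120 = 98.3% | 100% | 20/22 = 90.9% |
| 3 | 17/20 = 85.0% | 97.0% | 57/60 = 95.0% | 117/120 = 97.5% | 100% | 20/23 = 87.0% |
| 5 | 15/20 = 75.0% | 95.0% | 55/60 = 91.7% | 115/120 = 95.8% | 100% | 20/25 = 80.0% |

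Exact (Clopper-Pearson) 95% intervals for HbSS sensitivity are 75.1% to 99.9% at 19/20, 68.3% to 98.8% at 18/20 and 62.1% to 96.8% at 17/20.

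**Errors in both directions.** If y of the 20 HPLC-labelled HbS/β-thalassemia are truly HbSS, an error-free Gazelle has overall accuracy (120 − x − y)/120. With x = y = 4 this is 112/120 = 93.3%.

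**Precision of a pooled class.** With HbSS and HbS/β0 together, the class holds between 20 participants (no β0 cases) and 40 (all HbS/β-thalassemia are β0). A perfect result then has a lower exact 95% limit of 83.2% (20/20) to 91.2% (40/40).

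**The case against.** The plan states throughout that results are relative to HPLC (sections 3.0, 5.0 and 6.3), so it can be said to promise nothing more. Section 1.2 is background text. It says difficult, not impossible, does not name HPLC, and concerns HbS/β0 only. HbS/β+ keeps some β-chain production, and since the mix is not given, the affected share may be small.

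Much of this stands, and it sets the scope. The figures remain readable as agreement with HPLC. The section 1.2 reason carries over to HPLC only because that reason is the shared hemoglobin pattern and no assignment rule in the plan overcomes it. It does not reach HbS/β+.

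Three stronger readings are tempting, and the documents do not support them.
- A reader might infer that the Gazelle results as a whole cannot be interpreted. The sensitivities for HbAA, HbAS, HbA/β-thalassemia and Hbβ/β-thalassemia, and HbS detection by variant, are untouched by this confusion. Overall accuracy stays above the 90% of hypothesis 1 over the range shown.
- A reader might infer that the neural network evaluation fails for the same reason, since section 7.8 says "the ground truth will be derived from results from the gold standard test (HPLC"). Section 6.3 lists only HbAA, HbAS, HbSS and Overall for automated sickling, so the network is not scored on an HbS/β-thalassemia class. Section 13 already says that it is unclear whether the sickling test can separate these forms.
- A reader might infer that the target of more than 95% in section 4.0 must fail, because one mislabel gives exactly 95.0% for HbSS. That target is for detecting SCD, SCT and β-thalassemia and is not stated per phenotype. Section 1.1 counts HbS/β0 as a form of sickle cell anemia, so SCD detection on that definition does not depend on the split, although section 7.2.1 labels the SCD group HbSS.

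Writing down an HPLC assignment rule would make the labels reproducible, but would not show that they are right.

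**Conclusion.** The concern holds in a limited form. For samples with HbS and no HbA, the planned Gazelle sensitivity and specificity for HbSS and for HbS/β-thalassemia, and the variant-level β-thalassemia specificity, measure agreement with HPLC. They cannot be presented as accuracy for the true phenotype.

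Under the one-directional assumption of 1 to 5 mislabels in 20, the effect on a perfect test runs from 95% down to 75% for HbSS sensitivity and from 98.3% down to 91.7% for variant-level β-thalassemia specificity. A test that shares the errors shows 100%. Overall accuracy moves only to between 99.2% and 95.8%. The size rests entirely on the assumed rate. The direction of the bias and the share of HbS/β-thalassemia participants who are β0 are unknown. The matter should be settled before analysis, but it does not threaten hypothesis 1 at these rates.

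**What to change.** Amend section 6.3 as follows, before any results are seen.

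1. Define from HPLC a class of HbS present with HbA absent (HbSS or HbS/β0), and base the Gazelle phenotype accuracy claim for these samples on it. Section 6.3 already analyses HbA and HbS for Gazelle, so the class can be formed for both tests.
2. Report HbS with β-thalassemia and HbA present as a separate class, stating that its size is unknown and may be small.
3. Keep the planned HbSS and HbS/β-thalassemia rows, but label the split within the HbA-absent class as positive and negative percent agreement with HPLC.
4. Report the variant-level β-thalassemia metrics as planned and also with the HbA-absent HbS samples left out. Reference negatives are then the 40 HbAS and HbAA participants. Reference positives are the 40 Hbβ/β and HbA/β participants plus any HbS/β-thalassemia participants with HbA.

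The cost is SAP wording and one extra table, with no new test, participant or blood draw. The price in content is that no accuracy claim is made for HbSS versus HbS/β0, although compound forms are part of the study's rationale.

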#### 1.3 Global burden of disease

Over the next 30 years, it is estimated that 15 million babies will be born with SCD globally, and 50-90% of infants born with SCD in low-income countries will die before 5 years of age [6]. The burden of the disease is much greater in lower-resource settings [4], with around 90% of SCD occurring in low- and middle-income countries [7]. The highest prevalence has been found in sub-Saharan Africa, where approximately 230,000 children are born with SCD every year (0.74% of births in the region). In contrast, 2600 and 1300 children are born with SCD in North America and Europe, respectively [3]. In addition to screening for SCD, it is also essential to screen for SCT (heterozygous HbAS) because parents with SCT can give birth to children with SCD (homozygous HbSS or compound heterozygous forms). The number of babies born with SCT worldwide is estimated to be approximately 5.5 million, and the prevalence is estimated to be 2-30% in African countries [4]. Additionally, around 130,000 children are born with severe hemoglobinopathies such as HbSC and thalassemia annually [8].

In countries with newborn screening and treatment options, like the US and UK, the survival of children with SCA is similar to that of healthy children and adults can live up to their sixties [5]. However, in low-resource settings without newborn screening and treatments such as penicillin prophylaxis and pneumococcal immunization, the mortality rate for children with SCD is tremendously high [4]. In addition, the mortality rates are inaccurate due to lack of adequate screening, and improper diagnosis and management – SCD can be a predisposing factor for

deaths resulting from pneumonia, malaria, tuberculosis, HIV, and diarrheal disease [4], [8]. SCD does not just adversely affect the people involved, but also their families, with increased financial and psychosocial burden [8].

The number of people with SCD is expected to increase worldwide and by 2050, the number of babies affected is estimated to increase by 30%, thus increasing the health burden of the disease [4], [5]. In high income countries, the increase can be attributed to increase in life expectancy due to newborn screening, hydroxyurea treatment, and penicillin prophylaxis. In low-income and middle-income countries, this increase is due to epidemiological shifts such as public health improvements, and changes in population distribution, mortality, fertility, life expectancy, and infant mortality [1], [5]. As the burden of the disease increases, early detection of the disease is a critical first step towards managing the disease, especially in lower-income countries.

# 1.4 Need for screening/diagnosis in remote and rural settings

One of the first steps to addressing SCD in low-income countries is to break the diagnostic barrier. Since current laboratory techniques are too expensive to enable timely and equitable diagnosis, low-cost and rapid point-of-care diagnostic devices are required for early detection [9]. There have been promising pilot programs for neonatal screening in many sub-Saharan countries, however, few have translated to sustainable national programs. Newborn screening has shown high cost-effectiveness in Angola, and there is also compelling evidence of reduced infant mortality. However, most SCD detection and management programs are located in urban areas, and not in rural areas, where the prevalence is higher (as observed in rural populations of Africa and marginalized tribal populations in India) [4]. Thus, cost-effective screening and management services need to be prioritized in rural and remote settings to address the disparity.

Government support is vital to help patients detected with the disease in low-income countries. The cost of one SCD-related hospitalization exceeds the average monthly income of a household in African countries [8]. A one-month supply for hydroxyurea treatment in Ghana costs around USD \$100, which the government recently planned to subsidize as part of the Ghana's national health insurance scheme [6]. Even the Nepalese government has provisioned NRs 1,00,000 (Nepalese Rupees) for health care related expenses to patients identified with SCA [10]. However, with limited screening programs in rural/remote areas, most of the affected patients do not have access to such initiatives, yet. For maximizing impact of current government initiatives and for encouraging new sustainable government programs, low-cost and accurate SCD screening and diagnostic techniques must be implemented in rural and remote settings.

In areas where HbS is prevalent with other hemoglobin variants (such as  $\beta$ -thalassemia, HbC, etc.), it is essential to identify all the hemoglobin variants possible. If screening techniques that only detect HbS are used in such areas, then compound heterozygous cases (such as HbS/ $\beta$ -thalassemia) could be wrongly diagnosed. Additionally, asymptomatic heterozygous cases (such as HbA/ $\beta$ -thalassemia) may be missed in the screening tests for HbS, and parents with such heterozygous cases can still possibly pass on the variant gene to their children to result in compound heterozygous forms of SCD. Recent studies have indicated a high prevalence of  $\beta$ -thalassemia in Nepal, with approximately 26% - 70% of hemoglobinopathies involving  $\beta$ -thalassemia [11], [12]. Therefore, screening techniques in Nepal should ideally include detection of  $\beta$ -thalassemia in addition to SCD/SCT.

## 1.5 Conventional screening and diagnosis

The following techniques have been commonly used to detect hemoglobin S (HbS) related to SCD or SCT.

**Sickling test**: The presence of hemoglobin S can be demonstrated in a sickling test, where red blood cells change their shape from round bi-concave shape to sickled shape, under conditions of hypoxia or deoxygenation. When a drop of blood is sealed (using petroleum jelly/paraffin wax mixture or nail lacquer) between a glass slide and a cover slip, the metabolic activity of white blood cells causes deoxygenation, which induces sickling after a few hours, if HbS is present. The deoxygenation can be accelerated by adding a reducing agent such as sodium metabisulphite or sodium dithionite. Sickling can be induced using a reducing agent within 30 minutes to an hour for SCD and SCT, and the changes in morphology of red blood cells can be observed under a microscope, to distinguish SCD and SCT individuals from healthy participants [2], [13]. The sensitivity of the sickling test ranges from 65% [14] to 97.3% [15] and the specificity ranges from 96% [14] to 99.6% [15]. The sickling test, which is relatively inexpensive, was predominantly used as a screening test for HbS, but has mostly been replaced by the solubility test.

**HbS solubility test**: The solubility test relies on the principle that hemoglobin S, when deoxygenated, is insoluble in a high molarity phosphate buffer, which forms crystals that refract light and causes the solution to turn turbid [2]. Sickle solubility tests provide positive results for cases of SCD and SCT beyond early infancy – for early infancy (infants less than 6 months) the percentage of HbS can be below 20%, which could result in false negative tests [13]. The sickle solubility test, whether positive, negative or ambiguous, should be followed up by a confirmatory test, such as hemoglobin electrophoresis. The follow up tests are required to confirm the presence of HbS, distinguish SCT from SCD, or identify false negative cases due to low HbS concentration or technical error [13]. For rapid results or for emergency cases, the sickle solubility test can be combined with a blood count and a blood film analysis to distinguish SCT from SCD with reasonable accuracy. The sensitivity of the solubility test ranges from 45% [14] to 99% [15] and the specificity ranges from 90% [14] to 99.9% [15].

**Hemoglobin electrophoresis (HE)**: HE relies on the principle that proteins can separate when placed in a charge gradient and can be visually differentiated using protein or heme stains. Several media can be used for performing HE to detect variant hemoglobin, such as cellulose acetate membrane, filter paper, starch gel, citrate agar gel or agarose gel. In the past, hemoglobin electrophoresis was the most common method to initially detect variant hemoglobins, but is currently replaced by high performance liquid chromatography (HPLC) and capillary electrophoresis (CE). Nevertheless, the technique still serves as an essential confirmatory test [13].

Capillary electrophoresis (CE): CE separates normal and variant hemoglobin in alkaline buffers inside capillary tubes. Due to the use of capillary tubes and slightly different pH, the voltage used is higher and the run-time is shorter than other HE techniques. The zone or position of hemoglobin variants with respect to hemoglobin A is used to identify types of hemoglobin. CE only uses small volumes of blood, thus is beneficial for neonatal screening programs [2], [13].

**High performance liquid chromatography (HPLC):** HPLC is currently a common initial diagnostic technique for hemoglobinopathies in laboratories of high-income countries. The process used in HPLC begins with a mixture of hemoglobin molecules with a net positive charge

adsorbed onto a negatively charged stationary region. This is followed by elution of the molecules by a liquid with increasing amounts of cations, which compete with the hemoglobin molecules. As the adsorbed hemoglobin molecules get eluted, they get optically detected. The type of hemoglobin is identified by the characteristic amount of time (retention time) taken for the hemoglobin molecules to be eluted [13]. Although HPLC equipment and reagents cost more than other electrophoresis techniques, the labor costs are reduced due to increased automation, thus resulting in similar overall costs. HPLC also utilizes small sample volumes (around 5  $\mu$ I), making it useful for neonatal screening [2].

